6.2 Randomized Intervention Study

General study design and justification of design

This is a pragmatic cluster randomized controlled clinical trial investigating a new algorithm combining PCT measurement and lung ultrasonography results for the management of LRTIs among adults in GPs practices. Every consecutive patient meeting the inclusion criteria will be included in the study. All patients will be evaluated by the GP at the time of enrolment (day 0) and will have follow-up evaluations on day 7 and 28 via a phone interview by the study team to ask for the presence of LRTI symptoms, of side effects from antibiotics, secondary antibiotic use, number of follow-up visits, secondary hospitalization or death (Figure 2). In case of clinical deterioration, the patient will have a follow-up evaluation at any time, if possible with the same GP. We plan to enrol patients for a period of 15 months to reach the estimated sample size.

Methods of minimising bias

The study will be randomized. To avoid contamination between arms, randomization will be performed at GP level and only one GP per practice will be included. The cluster effect related to GP was taken into account while calculating the sample size and the outcome measures.

Details concerning GPs recruited in the study will be entered in a database using REDCap[©]. The randomization module of the REDCap software will then be used to attributed each of the GPs to one of the three study arms. We will perform a simple randomization using a 1:1:1 ratio.

[figure not shown]

Figure 2: Study design of the randomized intervention study

Study Setting

This study will be carried out in GPs practices located in different Swiss regions to ensure a representation of different cultural areas (German-speaking part (Bern) and French-speaking part of Switzerland (Vaud, Neuchâtel, Fribourg, Valais and Jura)). Each participating GP will be responsible to enrol consecutive eligible patients (total of 15 patients) in the study

These regions have been chosen because of good collaboration with a strong network of GPs during previous studies which assures the feasibility of the study [8, 9]. These regions have also been chosen to assure representativeness regarding differences in antibiotic prescription practices [37]

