In case of elevated PCT result ($\geq 0.25 \mu\text{g/L}$), a lung ultrasound will be performed to look for the presence of a lung infiltrate or consolidation suggesting the presence of CAP (Figure 3). Lung ultrasonography using the Phillips© Lumify portable ultrasound with a L12-4 (convex) transducer will be performed. The ultrasound will be provided to the GPs by the study team.

The lung ultrasound will be done following international evidence-based recommendations for point-of-care lung ultrasound using a ten points sonographic technique and the criteria for positive scan and positive examination for the diagnosis of pneumonia [39, 40]. The lung ultrasound is expected to last for 15 minutes.

Antibiotics will be prescribed only if a lung infiltrate or consolidation is identified during lung US. The choice, dosage and duration of antibiotic treatment will be left to the discretion of the GP.

Naso-pharyngeal swabs and venous blood samples will be systematically collected for further exploratory analysis. Sputum will also be collected if the patient is able to produce it.

Arm 2: PCT

GPs randomly assigned to the PCT arm will be responsible to recruit patients fulfilling the inclusion criteria and manage them using the PCT result.

GPs in this group will also receive training detailed training (described in section 8.2.1) on the epidemiology and management of pneumonia in Switzerland as part of the intervention.

The PCT point-of-care test will be performed, as described above, to decide on antibiotic prescription. Antibiotics will be prescribed only in case of elevated PCT ($\geq 0.25 \mu\text{g/L}$) (Figure 3). The choice, dosage and duration of antibiotic treatment will be left to the discretion of the GP.

Naso-pharyngeal swabs and venous blood samples will be systematically collected for further exploratory analysis. Sputum will also be collected if the patient is able to expectorate.

Control Intervention (standard/routine/comparator treatment / medical device)

Arm 3: usual care arm

GPs randomly assigned to the usual care arm will be responsible to recruit patients fulfilling the inclusion criteria and will manage and treat these patients as they usually do (Figure 3). They will not receive any additional training.

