Transcripts will be read to identify abstract themes relating to the meaning of the text. After the identification of the main themes, these will be developed in a coding scheme that will be applied to the text. The codes will then be applied to the text of in an independent fashion by two different investigators. Software designed for qualitative analysis (QDA Miner[©] or Atlas.ti[©]) will be used.

Quantitative data

Quantitative data relating to the study processes will be obtained by questionnaires designed to assess different steps of the study process.

Clinical data will be collected as per protocol for the randomized trial

Randomized trial

All study participants will undergo clinical and laboratory evaluation at inclusion (Day 0) according to the arm to which they are allocated. The following data will be collected:

Clinical data collection

A short electronic case report form (eCRF) will be filled by the GP on a tablet computer provided by the study team. Data collected include demographic characteristics, medical history, symptoms and clinical examination findings. Whether or not the GP ordered supplementary tests for the management of the patient outside the scope the algorithm will be recorded.

Ultrasonographic (UltraPro arm) data collection

All US images captured will be digitally recorded and transferred via a secured internet connection along with relevant metadata to a secure server. For study quality control purposes, the quality of the image and the interpretation of a random sample of images will be evaluated retrospectively by an experienced radiologist.

Laboratory specimen collection

Blood samples

In the UltraPro and PCT arms, a total of 17.5 mL of whole venous blood will be drawn to perform the PCT POCT measurement and for the exploratory objectives.

50 µL of whole blood will be used for the POCT PCT measurement. The rest of the sample will be used for identification of novel host biomarkers and genetic (identification of SNPs in genes that regulate microvascular integrity and transcriptomics) analyses that will be done in batch after the completion of the study. This will be performed at the Sandra Rotman Laboratory in Ontario, Canada

The following table describes the nature of the biological sampling:

Tube	Volume	Storage	Aim
EDTA 7.5 ml	20µL of whole blood	None	POCT PCT measurement
	3 x 1000 µL of whole blood	-80°C	SNPs analysis Biobank
EDTA 7.5 ml	3 x 1000 µL of plasma	-80°C	Novel host biomarkers Biobank

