11.2 Determination of Sample Size

The sample size was calculated to assess a decrease in antibiotic prescription of at least 15% between the UltraPro and the PCT arms as well as 15% between the PCT arm and usual care.

The proportion of patients receiving antibiotics with the usual care is estimated to be around 60% and to decrease to 45% using PCT and to 30% combining PCT and ultrasound. These numbers have been extrapolated from the subgroup of patients with LRTI in a study at primary care level in the Netherlands [3].

A study sample of 14 GPs and 15 patients per GP in each arm (210 patients per arm and a total of 630 patients) gives a power of 80% to detect a decrease in antibiotic prescription from 60% (usual care) to 45% (PCT), and from 45% (PCT) to 30% (UltraPro), with 5% level of significance, when adjusting for clustering at practice level (intracluster coefficient 0.06) [3]. This sample size guarantees a power of 80% to prove non-inferiority in terms of duration of activities restriction (non-inferiority margin=1 day, standard deviation=4 days) as well as of composite adverse outcome (probability in the “usual care” arm 0.05 with a non-inferiority margin of 0.02). Simulations used to determine the sample size are shown in the following figures.

[figure not shown]

Figure 4: Statistical simulations used to determine sample size

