11.4 Planned Analyses

Datasets to be analysed, analysis populations

The analysis will be performed in intention to treat (pragmatic trial). The analysis population will comprise all patients included by the randomised GPs. The primary analysis will include all patients enrolled in the study, irrespective of follow-up. Patients who are lost to follow-up will be considered as having had a clinical failure, an adverse outcome and duration of disease equal to the maximum duration measured in the other patients. Patients in whom GPs did not follow the respective algorithm recommendation and/or who did not have complete telephone follow-up will be excluded from the per-protocol analysis.

Primary Analysis

Odds ratio of antibiotic prescription between 2 groups as well as the difference in proportion of patients prescribed an antibiotic by day 28 using logistic regression corrected for variation at the GP level (generalized linear mixed effect)

Secondary Analyses

The following statistical analyses are planned:

- Difference between the mean number of days with restricted activities by day 14 using linear mixed effect regression
- Difference between the mean number of medical consultations by day 28 using linear mixed effect regression
- Odds ratio of adverse outcome between 2 groups as well as the difference in proportion of patients with adverse outcome and clinical failure using logistic regression corrected for variation at the GP level (generalized linear mixed effect)
- Difference between the mean daily symptom scores measured in the different arms. The effects of the interventions on recovery will be studied by comparing the slopes of symptom scores over time between arms
- Difference in the mean duration of total time spent in the practice using linear mixed effect regression
- Difference in levels of satisfaction of providers and of patients between arms
- Difference in the mean cost per arm using linear mixed effect regression
- Diagnostic performance of:
 - individual host biomarker(s) based on crude positive and negative likelihood ratios, and on the area under the curve of receiver operator characteristic (ROC) curves, to predict the development of a life-threatening disease, clinical failure, or the presence of pneumonia (using a clinical diagnosis).

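### The primary model is valid, but for UltraPro v PCT it leaves unused the baseline PCT value that both arms measure before they diverge: a cheap improvement of uncertain size

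*Combined protocol and SAP*

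**What the plan says.** Section 11.4 (Primary Analysis) gives an odds ratio and a difference in the proportion "prescribed an antibiotic by day 28 using logistic regression corrected for variation at the GP level (generalized linear mixed effect"). The synopsis says the same. Neither names a fixed covariate. Baseline characteristics are only to be described by arm.

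Section 8.1 has UltraPro GPs measure PCT first and scan only at 0.25 µg/L or above. For the PCT arm, "The PCT point-of-care test will be performed, as described above, to decide on antibiotic prescription", with the same cut-off. No study PCT is planned in usual care, and no venous blood is drawn there.

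Section 8.5 shows what else is recorded at day 0: "Data collected include demographic characteristics, medical history, symptoms and clinical examination findings". Section 6.2 allocates GPs by simple randomisation, without stratification. It says that the regions were chosen to "assure representativeness regarding differences in antibiotic prescription practices".

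Section 11.2 powers two contrasts equally, "from 60% (usual care) to 45% (PCT), and from 45% (PCT) to 30% (UltraPro"), and calls neither the main one.

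**The concern.** Under the algorithm, a patient with low PCT is managed alike in the UltraPro and PCT arms. The ultrasound can change prescribing only among patients with raised PCT. A model without PCT treats the large prescribing gap between the two PCT strata as noise, and carries any difference between arms in the share with raised PCT into the estimate.

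Such a difference is plausible. Only 14 GPs per arm are allocated, without stratification. They recruit after allocation and know their arm, and only UltraPro GPs face a scan expected to last 15 minutes. At stake are the precision and robustness of the one contrast that isolates ultrasound.

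**Working it through.** **1. The plan's own power.** Section 11.2 plans for "A study sample of 14 GPs and 15 patients per GP in each arm (210 patients per arm and a total of 630 patients"). Its claimed power for each of the two contrasts is 80%, and the level and clustering are stated as "with 5% level of significance, when adjusting for clustering at practice level (intracluster coefficient 0.06"). A two-sided test is assumed.

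- Design effect = 1 + (15 − 1) × 0.06 = 1.84. Effective n = 210 / 1.84 = 114.1 per arm.
- Power = Φ{[0.15 − 1.96 √(2p̄(1 − p̄)/n)] / √([p₁(1 − p₁) + p₂(1 − p₂)]/n)}.
- 45% v 30%: (0.15 − 1.96 × 0.0641) / 0.0633 = 0.385, so 65%.
- 60% v 45%: (0.15 − 1.96 × 0.0661) / 0.0654 = 0.313, so 62%.

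Cluster-level simulation gives 62% and 59%. The stated 80% is recovered to within 2 points (81.3% and 78.9%) if 0.06 is read as a GP variance on the logit scale (coefficient about 0.018, design effect 1.25). That is a separate matter, but it leaves little power to spare.

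**2. The share with raised PCT.** It is not given. If a fraction *a* of raised-PCT and *b* of low-PCT patients in the PCT arm are treated, the planned 45% implies a share of (0.45 − *b*)/(*a* − *b*):

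- 75/25: 0.20/0.50 = 40%
- 80/20: 0.25/0.60 = 41.7%
- 85/15: 0.30/0.70 = 42.9%
- 90/10: 0.35/0.80 = 43.75%
- 100/0: 45%

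**3. Power without and with adjustment.** The simulations used 14 v 14 GPs × 15 patients, 45% v 30%, and a t-test on GP means, with 3,000 to 5,000 trials per row. The risk difference was taken with and without standardisation for PCT ≥ 0.25. "Habit" means that GPs differ in readiness to prescribe; "mix" means that they differ in the share of patients with raised PCT.

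| Treated, raised/low (PCT arm) | Share raised | GPs differ by | Intracluster coefficient (PCT arm) | Power, unadjusted → adjusted | Gain (points) |
|---|---|---|---|---|---|
| 75/25 | 40% | habit | 0.060 | 58.4 → 60.8% | 2 |
| 80/20 | 41.7% | habit | 0.049 | 60.3 → 65.5% | 5 |
| 85/15 | 42.9% | habit | 0.053 | 55.9 → 62.8% | 7 |
| 80/20 | 41.7% | both | 0.046 | 63.9 → 72.5% | 9 |
| 90/10 | 43.75% | habit | 0.036 | 58.7 → 69.3% | 11 |
| 90/10 | 43.75% | both | 0.042 | 64.7 → 83.3% | 19 |
| 90/10 | 43.75% | mix | 0.048 | 71.2 → 97.9% | 27 |
| 100/0 | 45% | mix | 0.059 | 64.6 → about 100% | 35 |
| 90/33.75 | 20% | – | 0.046 | 65.1 → 68.9% | 4 |
| 90/40 | 10% | – | 0.055 | 62.3 → 64.6% | 2 |
| – | 5% | – | 0.061 | 63.5 → 64.5% | 1 |

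The marginal difference stays at about 15 points in every row. The gain is largest when the clustering itself comes from PCT mix, because adjustment then removes it. If low-PCT patients are treated alike in both arms, a 15-point difference needs a share of at least 15%. The two lowest rows therefore also need prescribing to differ between arms among low-PCT patients.

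**4. Imbalance.** Suppose ultrasound has no effect, prescribing is 90/10, and the arms differ by 10 points in the share with raised PCT. The unadjusted bias is 0.10 × (0.90 − 0.10) = 8 points, with 29% false rejections. Adjusted, the bias is 0 and rejections are 5%. A second set of runs gave 18% against about 6%. With balanced arms, both analyses hold the level (5.5% and 4.7%).

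**5. Where a naive fit fails.** With full adherence, no low-PCT patient and every raised-PCT patient in the PCT arm is treated. A logistic model with PCT then separated in 100% of simulated trials.

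**The case against.** A GP-corrected model without covariates is valid under randomisation. Chance imbalance is sampling variation that its standard error already carries. For example, at 85/15 with a 43% share, one standard deviation of imbalance, taking patients as independent, is √(2 × 0.43 × 0.57/210) = 4.8 points. The stratum differences are 0.70 in the PCT arm and 0.35 in UltraPro, mean 0.525, so the estimate moves by 4.8 × 0.525 = 2.5 points. That is noise, not bias. This stands, and it rules out the stronger inference that the primary analysis is wrong.

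A reader might also infer that adjustment is free. It is not. PCT cannot enter a three-arm model or the usual-care contrast. A PCT-adjusted odds ratio is a different, conditional quantity. Separation is likeliest where the gain is largest. Section 11.5 keeps patients with incomplete algorithm components in the intention-to-treat analysis, so PCT may be missing. The simulations tested a cluster-level estimator, not the planned mixed logistic model.

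A reader might infer from the algorithm that power approaches 100%. Section 8.3 allows GPs to depart from it, and the outcome runs to day 28, so it includes later prescriptions. The share is also unknown. The planned 45% points to 40-45% under good adherence, and a 10% share would need about 40% of low-PCT patients treated against the rule. But section 3.1 cites 21.5% and 25% prescribing under PCT guidance in two primary-care trials (of all acute respiratory infections), and 5-12% pneumonia. Neither side settles the share.

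Finally, PCT is measured after GPs are randomised and patients selected. Adjusting for it does not remove selective recruitment in general. Consecutive enrolment and the recording of prescriptions for all screened patients already address part of that.

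**Conclusion.** The point holds as an improvement in efficiency and robustness, not as the correction of an error. For UltraPro v PCT, a strong covariate that is already collected goes unused.

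The gain is about 2 to 11 points of power at a coefficient of roughly 0.03-0.06, if 40-45% have raised PCT and 75-90% of raised and 10-25% of low-PCT patients in the PCT arm are treated. It is larger with near-full adherence or where GPs differ mainly in PCT mix, and small (1 to 4 points) at a share of 20% or less. These shares and adherence values are assumptions, as are the two-sided test and equal cluster sizes. Protection extends to imbalance in PCT mix only.

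Two wider readings are not supported. Section 11.2 does not make UltraPro v PCT the main contrast. Nor has any gain been shown from adjusting the usual-care contrast for age, region or entry signs. Those signs are recorded by GPs who know their arm, and section 9.2 plans no standardised measurement of vital signs.

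**What to change.** In 11.4, before any outcome data by arm are seen, pre-specify for UltraPro v PCT:

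- a standardised (marginal) risk difference adjusted for the day-0 PCT result (≥ 0.25 yes/no) with a PCT-by-arm term, keeping the GP effect; PCT repeated at later visits is not used;
- an estimator that tolerates separation, such as cluster-level standardisation or a penalised fit;
- a rule for missing PCT that keeps every intention-to-treat patient;
- the unadjusted GP-corrected model, reported alongside.

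Leave PCT v usual care as planned. Adjusting it for age or region is optional.

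The cost is a paragraph in the analysis plan and somewhat more programming, with no new data. The downside is that the two powered contrasts would use different covariates, which the report should say.

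### Section 11.4 names no test or reference distribution for a mixed logistic model resting on 28 GPs per contrast; the usual large-sample inference would reject about 6–7% of the time at a nominal 5%

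*Combined protocol and SAP*

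**What the plan says.** The primary analysis in section 11.4 is a single sentence. It asks for the "Odds ratio of antibiotic prescription between 2 groups", together with the difference in the proportion prescribed an antibiotic by day 28, "using logistic regression corrected for variation at the GP level (generalized linear mixed effect"). The statistical considerations in the synopsis repeat this.

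Section 11.2 fixes the scale: "A study sample of 14 GPs and 15 patients per GP in each arm", "with 5% level of significance, when adjusting for clustering at practice level (intracluster coefficient 0.06"). Section 6.2 makes the GP the unit of randomisation and adds: "We will perform a simple randomization using a 1:1:1 ratio".

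No part of section 11 names the test statistic (Wald or likelihood ratio), a degrees-of-freedom rule, a small-sample correction, a cluster-level check, the estimation method or the software. Section 11.2 does not say whether the 5% level is one- or two-sided. Its coefficient of 0.06 carries no scale.

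**The concern.** In a cluster trial, the information on an arm contrast is limited by the number of clusters. The between-GP variance is itself estimated, here from 28 GPs per contrast. A large-sample z or chi-squared reference treats that variance as known. In addition, the maximum-likelihood estimate of the variance is biased downward. Both effects make standard errors and critical values too small.

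The p-value and confidence interval of the primary contrasts are at stake. The plan commits to a 5% level, but the model it names does not deliver that level unless something is added. The same applies to the linear mixed models for the secondary outcomes if they are tested with z. Leaving the reference open also lets it be chosen after results are seen.

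**Working it through.** **Inputs.** From section 11.2: 14 GPs per arm, 15 patients per GP (210 per arm), 5% level, coefficient 0.06, rates of 60%, 45% and 30%. From section 11.4: two-group contrasts. Assumed: two-sided testing, 0.06 on the proportion scale, equal arms and equal cluster sizes.

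**The plan's own figure.** Design effect = 1 + (15 − 1) × 0.06 = 1.84; effective n = 210 / 1.84 = 114.1 per arm. Power = Φ[(0.15 − 1.96 × SE0) / SE1], with SE0 pooled and SE1 unpooled.
- 60% v 45%: SE0 = √(2 × 0.525 × 0.475 / 114.1) = 0.0661; SE1 = √((0.24 + 0.2475) / 114.1) = 0.0654; power 62.3%.
- 45% v 30%: SE0 = 0.0641; SE1 = 0.0633; power 65.0%.

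The stated 80% is therefore not reproduced from these inputs. One-sided testing gives 73.6% and 75.9%. Entering 0.06 as the random-intercept variance on the logit scale gives 80.3% and 83.1%, but that is only a guess at what was done. It is a separate matter. It is noted because the power cost below starts from about 65%, not 80%.

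**Analytic size.** A two-arm fit has 28 − 2 = 26 between-GP degrees of freedom; a single model for all three arms has 42 − 3 = 39.
- 2 × P(T26 > 1.960) = 6.08%, so a nominal 95% z interval covers about 93.9%.
- 2 × P(T39 > 1.960) = 5.72%.
- The t critical value on 26 df is 2.056. Then 1.960 / 2.056 = 0.954, so the z interval is 4.6% too short; conversely, 2.056 / 1.960 = 1.049, so the t interval is 4.9% wider.

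**Simulated size.** Mixed logistic model, maximum likelihood with 15-point Gauss–Hermite quadrature, no arm effect. The first three rows use 40,000 runs each (Monte Carlo SE 0.12 points) and the others 20,000 (0.17 points). The t reference has 26 df in the two-arm fits and 39 in the three-arm fit. Entries are rejection rates in % at a nominal 5%.

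| Setting | Wald z | Wald, t | Likelihood ratio | GP-level t-test |
|---|---|---|---|---|
| Two arms, rate 45%, ICC 0.06 | 6.63 | 5.49 | 5.98 | 5.02 |
| Two arms, rate 60%, ICC 0.06 | 6.69 | 5.53 | 6.05 | 5.05 |
| Two arms, rate 30%, ICC 0.06 | 6.74 | 5.59 | 6.15 | 5.04 |
| Two arms, 45%, ICC 0.06, beta-binomial data | 6.75 | 5.56 | 6.04 | 5.05 |
| Three arms, 45%, ICC 0.06 | 6.25 | 5.39 | 5.77 | 4.76 |
| Two arms, 45%, ICC 0.02 | 6.01 | 5.05 | 5.51 | 5.10 |
| Two arms, 45%, ICC 0.12 | 6.49 | 5.41 | 5.90 | 4.91 |
| Two arms, 45%, ICC 0.005 | 4.64 | 3.83 | 4.58 | 4.99 |

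A smaller separate run (4,000 data sets, Monte Carlo SE about 0.4 points) gave 6.8% for Wald z and about 5.8% with t on 26 df.

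At ICC 0.005 the GP variance is estimated as zero in about 54% of runs. The z test is then slightly conservative, and the t reference more so.

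**Cost in power.** Simulated with 10,000 runs per comparison, z against t on 26 df: 64.8% to 61.0% for 60% v 45% (3.8 points), and 67.5% to 63.9% for 45% v 30% (3.6 points).

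**The case against.** The strongest reply is that the protocol nowhere says Wald. A reader might infer that the plan prescribes a z test and that its 5% level is therefore certainly missed. The text does not support that: it names a model, not a test. The sample-size simulations in Figure 4 might show the test intended, and because the figure is not reproduced in the text available, nothing can be concluded from its absence. The size figures are therefore conditional on the usual large-sample output being used. What survives is that a likelihood-ratio test, the other common choice, also exceeds 5% at the planned coefficient, so the omission matters whichever of the two is run.

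A second tempting inference is that switching to a t reference restores 5%. It does not quite: 5.5–5.8% remains in the two-arm fits at 0.06.

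Third, the effect is small. With 26 df, only a z-based p-value between about 0.04 and 0.05 would change sides, and at a coefficient near zero there is no excess. That is fair and limits the weight of the point. But the sponsor planned on 0.06, and at 0.02 the Wald z test still rejects 6.0% of the time.

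Finally, 26 and 39 are planning values. Simple randomisation need not give 14 GPs per arm, and section 8.2 allows an arm 1 GP to be excluded after a second failed training test. Fewer GPs would make matters slightly worse: the analytic size is 6.3% at 22 df and 6.6% at 18 df.

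**Conclusion.** The point holds in conditional form. Section 11.4 leaves the reference distribution open, and with 28 GPs per contrast the usual large-sample inference gives a true size of about 6–7% at the planned coefficient: an excess of roughly 1–2 points, with 95% intervals about 5% too narrow. A single three-arm model reduces the excess without removing it (5.7% analytically, 6.25% simulated).

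This rests on two-sided testing, a proportion-scale coefficient of 0.06, and equal arms and cluster sizes. The simulations test the log odds ratio; they do not check a model-based interval for the difference in proportions, for which the plan gives no method either. The point should be settled before analysis. It does not invalidate the choice of model.

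**What to change.** Add to section 11.4:
- P-values and confidence intervals for arm contrasts from the mixed logistic model use a t reference with degrees of freedom equal to GPs analysed minus arms fitted (26 for a two-arm fit or 39 for the three-arm fit, if recruitment is as planned). State which fit is used.
- The linear mixed models for secondary outcomes use Kenward–Roger or Satterthwaite degrees of freedom.
- A GP-level t-test on each GP's proportion prescribed antibiotics is a pre-specified sensitivity analysis. It held about 5% in every setting simulated, and it gives an interval for the difference in proportions directly.

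The cost is a short addition to the analysis section, intervals about 5% wider and roughly 3–4 points of power. If the true coefficient is close to zero, the t reference is conservative (3.8% at 0.005). Nothing changes in recruitment, data collection or patient care.
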